5.1 Inclusion Criteria

1. Heart failure patients with reduced ejection fraction ($EF \leq 40\%$) as assessed by echocardiography at least 6 months prior to recruitment and NYHA Class ≥ 2
2. Patients implanted with ICD, CRTD/S or CRTP devices that are capable of recording the PVC burden and implanted ≥ 2 months prior to recruitment.
3. High risk for arrhythmic events at baseline identified by either PVC burden $\geq 2\%$ **or** ≥ 2 events of non sustained VT **or** ≥ 1 event of sustained ventricular tachycardia **or** need for anti-tachycardia pacing **or** defibrillation therapy, during a period of 2 months prior to recruitment.
4. Diagnosis of type 2 diabetes mellitus prior to informed consent
5. $HbA_{1c} \geq 7\%$ and $\leq 12\%$.
6. Signed and dated written informed consent by date of Visit 1 in accordance with GCP legislation.

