9.1 Sample size

The primary endpoint is the percentage of PVCs during the 2 months of empagliflozin treatment compared with the percentage of PVC on placebo. A sample size of 128 patients was selected based on the estimated effect of 10% reduction in the rate of arrhythmic events assuming a standard deviation of 40% in measured values, with alpha of 0.05 and power of 0.8 (2-sided test). The efficacy analysis will be conducted using an as treated approach and will be performed using the Wilcoxon signed-rank test, p value ≤ 0.05 will be considered significant.

The rationale for sample size calculation was based on detecting a difference of at least 10% in the reduction in rate of arrhythmic events from baseline between study treatments with 80% power and 5% significance level.

Sample size justification

When the sample size in each sequence group is 64, (a total sample size of 128) a 2 x 2 crossover design will have 80% power to detect a difference in Mean reduction of -10.0, assuming that the Crossover ANOVA MSE is 28.284 (the Standard deviation of differences, sd, is 40.0) using a two group T-test (Crossover ANOVA) with a 0.05 two-sided significance level.

Reference:

Senn, Stephen Cross-over Trials in Clinical Research (2nd Edition) Wiley (2002).

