9.2 Efficacy and Safety evaluation

General

All measured variables and derived parameters will be listed individually and, if appropriate, tabulated by descriptive statistics.

For categorical variables, summary tables will be provided giving sample size, absolute and relative frequency and 95% CI (Confidence Interval) for proportions by study treatment.

For continuous variables, summary tables will be provided giving sample size, arithmetic mean, standard deviation, median, minimum and maximum and 95% CI (Confidence Interval) for means of variables by study treatment.

All tests will be two-tailed, and a p value of 5% or less will be considered statistically significant.

The data will be analyzed using the SAS ® version 9.3 (SAS Institute, Cary North Carolina).

Analysis Populations

Safety Population: will include all randomized subjects who received any study drug.

Intention-to-Treat (ITT) Population: will include all subjects included in the safety population who provided at least one post-baseline assessment for the primary endpoint.

Per-Protocol Population: will include all subjects in the ITT population who complete the study in compliance with the protocol and have no major protocol violations.

9.2.1 Efficacy analysis:

The primary endpoint is the percentage of PVCs during the 2 months of empagliflozin treatment compared with the percentage of PVC on placebo.

The two-sample T-test or Non-parametric Wilcoxon-Mann-Whitney Rank sum test for independent samples (as is appropriate) will be applied for testing the carry-over effect in the primary endpoint between the two sequences.

If no carry-over effect will be observed, then The Paired T-test or non-parametric Signed-rank test for two means (as is appropriate) will be applied for analyzing the difference in the above changes between the tested treatment and placebo.

Otherwise, if a carry-over effect will be found statistically significant, then the MMRM model (Mixed-effect model for repeated measures) will be applied for analyzing the difference in the above reduction between the tested treatment and the placebo. The model will included terms for study arm (sequence), treatment and period as fixed effects, and subject nested within study arm as a random effect. Other covariates (such as age and baseline measures) will be included if they will be found different between the groups and affecting the outcome.

Secondary Endpoints:

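### The default primary test in 9.2.1 has no period term, although 9.1 sized the trial on a crossover test that removes period effects

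*Combined protocol and SAP*

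**What the plan says.** Section 9.2.1 (repeated in the Synopsis) first tests carry-over between the two sequences, then branches.

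- If no carry-over is observed: "The Paired T-test or non-parametric Signed-rank test for two means (as is appropriate) will be applied for analyzing the difference" between treatments. No period or sequence term is mentioned.
- "Otherwise, if a carry-over effect will be found statistically significant, then the MMRM model" is used instead. For that branch only, "The model will included terms for study arm (sequence), treatment and period as fixed effects", with subject nested within sequence as a random effect.

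Section 9.1 names two different tests for the same endpoint. Its opening paragraph says that the efficacy analysis "will be performed using the Wilcoxon signed-rank test". Its sample size justification says that with 64 per sequence "a 2 x 2 crossover design will have 80% power to detect a difference in Mean reduction of -10.0", "using a two group T-test (Crossover ANOVA) with a 0.05 two-sided significance level".

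No section gives an expected period effect, a test for one, or a dropout rate. Section 4.4.1 says that withdrawn subjects are not replaced.

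**The concern.** In a 2x2 crossover, a change in the outcome between period 1 and period 2 adds to the treatment difference in one sequence and subtracts from it in the other. The Crossover ANOVA compares period differences between sequences, so the change cancels. A paired t or signed-rank test on the pooled differences has no such step. With equal sequences the change goes into the standard error. With unequal sequences part of it goes into the treatment estimate.

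The plan already contains the suitable model, but reserves it for the branch with significant carry-over. Carry-over and period effects are different things, and absence of the first says nothing about the second. So the test expected to be used is not the one that was powered. What is at stake is the power, the confidence interval and possibly the bias of the only primary comparison.

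**Working it through.** **Inputs from 9.1.** Difference τ = 10 (absolute value), SD of differences 40, 64 per sequence, N = 128, two-sided alpha 0.05. The printed MSE of 28.284 equals 40/√2, so it is the root MSE and agrees with the SD of 40.

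**Assumed.** Period shift p = period-1 mean minus period-2 mean, set at 10, 20 or 30 in the same units. Unequal completers are set at 64 vs 52 and 64 vs 48. The documents give neither.

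**1. The plan's own figure.** SE = 40/√128 = 3.536 and noncentrality 10/3.536 = 2.83. The two-group t-test on period differences (126 df) gives power 80.1%, so the stated 80% reproduces. With no period shift, the paired t (127 df) gives 80.2%. The two tests are then practically equivalent.

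**2. Effect of a shift.** With n1 patients on empagliflozin first and n2 on placebo first, the empagliflozin-minus-placebo difference has mean (treatment effect + p) in the first sequence and (treatment effect − p) in the second. Hence:

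- bias of the pooled mean = p(n1 − n2)/N
- SD seen by the paired test = √(40² + 4p²·n1·n2/[N(N − 1)])
- true SE of the pooled mean = 40/√N, unchanged by p

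**3. Balanced, 64 vs 64.** Bias is 0. The paired test rejects when the mean exceeds 1.979 × its reported SE, while the mean varies with SE 3.536. For p = 20: SD = 44.76, reported SE = 44.76/√128 = 3.956, critical value = 7.83. Power = Φ((10 − 7.83)/3.536) = 73%. Type I error = 2[1 − Φ(7.83/3.536)] = 2.7%.

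| Shift p | Reported SE | Critical value | Paired-t power | Paired-t type I error |
|---|---|---|---|---|
| 10 | 3.645 | 7.21 | 78% | 4.1% |
| 20 | 3.956 | 7.83 | 73% | 2.7% |
| 30 | 4.426 | 8.76 | 64% | 1.3% |

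Simulation with normal data agrees. The period-adjusted test stays at about 80% power and 5% type I error throughout. Signed-rank power in simulation is about 76%, 71% and 59%.

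**4. Unequal, 64 vs 52 (N = 116).** Bias = 10 × 12/116 = 1.03 for p = 10, and 20 × 12/116 = 2.07 for p = 20. The sign depends on which sequence is short: with a 20-point fall, a true effect of −10 is estimated as about −12 or −8. For p = 20 type I error is about 5.2% by the formula and about 5.4% in simulation. When the bias opposes the effect, paired-t power is about 47%, against 76% with period adjustment.

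**5. Worst case, 64 vs 48 (N = 112), p = 20.** Bias = 20 × 16/112 = 2.86. Reported SE = 4.221, critical value = 1.982 × 4.221 = 8.36, true SE = 40/√112 = 3.780. Type I error = [1 − Φ((8.36 − 2.86)/3.780)] + Φ(−(8.36 + 2.86)/3.780) = 7.3% + 0.2%, about 7.5%. Simulations give about 7.5 to 8%, against about 5% for the adjusted test.

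**The case against.** The strongest reply is that nobody has shown a period effect and that the harm is small unless one is large. Much of this stands.

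- **Likelihood of a shift.** A reader might infer from "High risk for arrhythmic events at baseline identified by either PVC burden" and the alternatives listed with it that patients enter at a temporary high and must then decline. Section 5.1 does not support that. It sets thresholds joined by 'or', so a patient can qualify on tachycardia events with a low PVC burden. Regression to the mean would act mainly between the qualifying window and period 1. Section 7.1 has the counters reset at visit 2, so it becomes a period-1-to-period-2 shift only if the decline continues into treatment. Recent implantation and the glucose-drug changes in Appendix 1 are also possible sources of drift, but no section links either to PVC burden.
- **Size of the shift.** The shifts used are one to three times the planned effect. Read as percentage points of PVC burden, 20 or 30 would be hard to reconcile with entry at 2% and stratification at 4%. Hence the restriction to 9.1's own units.
- **False positives.** A reader might infer that the paired test inflates type I error. With balanced sequences it does the opposite. At 64 vs 52 the error stays near 5%. It rises clearly only when one sequence loses 25% and the other none, and no section projects that. Allocation is 1:1 in stratified blocks.
- **Power.** A reader might conclude that the 80% power is lost. At a shift equal to the whole planned effect, the loss is about 2 points.
- **Baseline.** 9.2.1 refers to changes without defining their baseline. A single common baseline would cancel in the within-patient difference and so would not remove a period shift.

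These points limit the expected size of the harm. They do not reconcile the test that was powered with the test that is specified, and no other section does so.

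**Conclusion.** The point holds as an inconsistency in the primary analysis with a conditional cost. The no-carry-over test in 9.2.1, like the signed-rank test in 9.1, ignores period. The test that justified N=128 does not. With balanced sequences the cost is conservatism: about 2, 7 or 16 power points for shifts of 10, 20 or 30, with no bias. With moderately unequal completers the cost is a bias of about 1 to 2 points on a planned effect of 10, in either direction, with type I error near 5%. Only the deliberately extreme 64 vs 48 case with a shift of 20 gives a bias of 2.9 and a type I error of about 7.5 to 8%.

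All these sizes rest on assumed shifts and completer numbers, on normal differences with SD 40, and on patients with both periods. If there is no period shift the two analyses perform alike, so adjustment gives up practically nothing.

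**What to change.** Before unblinding, amend the plan as follows:

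- In 9.2.1 and the Synopsis, make the period-adjusted analysis primary whatever the carry-over test shows. This is the Crossover ANOVA or mixed model with treatment, period, sequence and subject within sequence. For patients with both periods it is equivalent to the two-group t-test on period differences that 9.1 used.
- If a rank test is needed, specify the rank-sum test comparing period differences between sequences, not the signed-rank test.
- Delete the conflicting signed-rank statement in 9.1.
- Report the period-adjusted within-patient treatment difference with its 95% CI.

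The cost is a change of wording and about one degree of freedom (126 instead of 127). The sample size stays at 128, and no further data or patients are needed.

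### Sections 9.1 and 9.2.1 give different rules for the primary analysis, and the carry-over branch in 9.2.1 does not correct carry-over

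*Combined protocol and SAP*

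**What the plan says.** Three primary analyses appear.

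- **Section 9.1, first paragraph:** "The efficacy analysis will be conducted using an as treated approach and will be performed using the Wilcoxon signed-rank test". No condition is attached.
- **Section 9.1, sample size justification:** power is computed "using a two group T-test (Crossover ANOVA"), which is a period-adjusted comparison between sequences.
- **Section 9.2.1, repeated in the synopsis:** a two-sample t-test or rank-sum test for carry-over comes first. If it is negative, "then The Paired T-test or non-parametric Signed-rank test for two means (as is appropriate) will be applied". If it is positive, a mixed model is used: "Otherwise, if a carry-over effect will be found statistically significant, then the MMRM model (Mixed-effect model for repeated measures) will be applied". Its terms are given in 9.2.1: "The model will included terms for study arm (sequence), treatment and period as fixed effects", with subject within sequence as a random effect.

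Section 9.2 defines Safety, ITT and Per-Protocol populations. As treated is not among them, and 9.2.1 assigns none to the primary analysis.

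The response also varies. Section 9.2.1 opens with the on-treatment PVC percentage, then specifies a test "for analyzing the difference in the above changes between the tested treatment and placebo", although no change has been defined above it. Section 9.1 speaks of a difference "in the reduction in rate of arrhythmic events from baseline between study treatments". Covariates depend on the data: "Other covariates (such as age and baseline measures) will be included if they will be found different between the groups" and affect the outcome.

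**The concern.** A primary analysis should be fixed well enough that two statisticians with the same data would report the same p-value. Here they could differ on the test, the population, the response and the covariates, and each could cite the plan.

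The carry-over step has a further problem. It is there to protect the treatment comparison if the first drug's effect persists into the second period. If the model it switches to estimates the same quantity with the same bias, the step adds complexity and apparent reassurance but no protection.

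**Working it through.** **1. The plan's own figure.** Inputs from 9.1: difference -10, SD of differences 40, 64 per sequence, two-sided 0.05. SE = (40/2) × √(1/64 + 1/64) = 3.536; 10/3.536 = 2.83; noncentral t with 126 df gives 80.2% power, and 64 per sequence is the smallest number reaching 80%. The stated 28.284 is 40/√2, so it is the root MSE. The sample size reproduces and is not in dispute.

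**2. What each branch estimates.** Let δ be the treatment effect, π the period effect (period 2 minus period 1), and λ the carry-over of empagliflozin into a following placebo period. The expected empagliflozin-minus-placebo difference is δ - π - λ in the empagliflozin-first sequence (n1 patients) and δ + π in the placebo-first sequence (n2 patients).

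- Paired mean: δ + π(n2 - n1)/(n1 + n2) - λ·n1/(n1 + n2). With n1 = n2 this is δ - λ/2.
- Mixed model: sequence, period and treatment plus an intercept are four parameters for four cell means. The treatment contrast is ½[(δ - π - λ) - (-π - δ)] = δ - λ/2.

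With δ = -10, both give -7.5 at λ = -5 and -5.0 at λ = -10. Simulation (40,000 trials, correlation 0.5) gave a bias of +2.5 and +5.0 for both, and about the same in the trials that the pretest flagged (+2.4 to +2.5 and +4.9 to +5.1). On one simulated balanced data set the mixed model, the crossover contrast and the paired mean all gave -9.100. A carry-over term is no remedy: the design matrix with intercept, sequence, period, treatment and carry-over has five columns and rank 4.

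The identity needs complete balanced data. With 60 and 50 completers plus 4 and 14 one-period patients (assumed; period shift 10, carry-over -5), the two estimates differed by up to 1.3 in four test data sets. The λ/2 term stays in the model contrast.

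**3. How often the pretest fires.** Section 9.2.1 names the test but not the statistic; the usual sum over both periods is assumed. Its expected difference between sequences is λ. Its SE is √[(4σb² + 2σw²) × 2/64], with σw² = 28.284² = 800. The documents give no correlation.

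| Assumed correlation | SE | Power, carry-over 5 | Power, carry-over 10 |
|---|---|---|---|
| 0 | 7.07 | 10.8% | 28.9% |
| 0.5 | 12.25 | 6.9% | 12.8% |
| 0.8 | 21.2 | 5.6% | 7.5% |

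At correlation 0.5 and δ = -10, the whole 9.2.1 rule rejects in 80.3% of trials without carry-over, 55.4% at λ = -5 and 28.3% at λ = -10. With neither a treatment effect nor carry-over it rejects in 4.9%.

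**4. The t-test or the rank test.** If the smaller p-value were taken, simulated type I error is 6.1% (normal), 6.7% (t with 3 df) and 7.5% (skewed); another skewed run gave 7.9%. For power, assume lognormal burdens with median 4%, between-patient log-SD 0.8-1.0, within-patient log-SD 0.5-0.6 and a 10% relative reduction. The paired t-test then has 14-23% power and the signed-rank test 23-31%. The gap is about 8-10 points, reaching about 13 in one rerun of these settings. These figures compare the tests; they do not estimate this trial's power. On the plan's normal scale the gap is 1-2 points.

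**5. The omitted period term (lesser).** At balance a period effect only inflates the SD that the paired t-test estimates, to √(1600 + π²). For π = 5, 10 and 20, power is 79.6%, 78.5% and 72.8%, and type I error 4.7%, 4.2% and 2.8%: conservative, not biased. With 60 versus 50 completers the bias has size π × 10/110, or 0.45, 0.91 and 1.82.

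**6. The response.** Section 7.1 defines PVC burden with formulas and reads efficacy at visits 3 and 5. Raw burden and absolute change from one common baseline give the same within-patient difference, because the baseline cancels. Change from a separate baseline in each period, or percent change, does not. The plan does not say which is meant.

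**The case against.** The strongest reply is that the plan is looser than it is contradictory. The signed-rank test in 9.1 is one of the 9.2.1 options, the endpoint measure is fully defined, and 9.2.1 does open with the on-treatment comparison. That stands, and it limits the point to differing rules, not unrelated analyses, and to raw burden versus change, not an undefined endpoint.

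Four stronger readings are tempting but are not supported:

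- A reader might infer the familiar type I inflation of two-stage crossover testing. That comes from falling back on period 1 data. Both branches here use within-patient contrasts, and the rule holds its level without carry-over.
- A reader might infer that the ambiguous response costs much of the power: separate independent baselines would raise the SD to 40 × √2 = 56.6 and cut power to about 51%. But 9.1 attaches the SD of 40 to a difference in mean reduction, so it may already be for baseline-adjusted differences.
- A reader might infer a gap between the t-test and the rank test well above 10 points. That appears when relative effects of 15-20% are assumed; section 9.1 plans on 10%. An analyst facing plainly skewed data might also choose the rank test anyway.
- A reader might infer that switching branch never changes the estimate. That holds only for complete balanced data. Withdrawals are not replaced (4.4.1), and the ITT definition admits patients with one period.

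**Conclusion.** The concern holds and should be fixed. Sections 9.1 and 9.2.1 state different primary rules, the population and the choice between t-test and rank test are left open, and the mixed-model branch leaves a bias of about half the carry-over. That last result is algebra and needs no assumed values. The pretest's detection rate (about 7% for a carry-over of 5 and 12-13% for 10) assumes correlation 0.5. The 6-8% type I error assumes that the smaller p-value is taken, which the plan neither directs nor prevents. The 8-10 point power gap assumes skewed burdens and a 10% relative effect, and grows with larger effects. The missing period term is secondary. Nothing here shows that 128 patients is wrong.

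**What to change.** In 9.2.1 name one period-adjusted primary analysis, and make 9.1 and the synopsis match it. The response is the on-treatment PVC percentage in each 8-week period (visits 3 and 5), analysed by randomised sequence.

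- **Preferred:** the 9.2.1 mixed model (sequence, period, treatment, random subject) on log burden, in the ITT population including one-period patients. Fix one offset before unblinding. It is needed because 5.1 admits patients through arrhythmic events with burden possibly near zero, and in assumed low-burden mixes an offset of 0.1 rather than 0.5 moved power by 3-4 points. State that the estimate is a relative (ratio) effect, not the mean difference in 9.1.
- **Alternative:** a rank-sum test between sequences on the period 2 minus period 1 difference. Describe the population as ITT patients with both periods. Half the Hodges-Lehmann shift is the estimate, because the shift between sequences is twice the treatment effect; say that it is a location shift and not a mean difference. Give the mixed model as a sensitivity analysis.

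Delete the carry-over pretest as selector, the unspecified choice between t-test and rank test, the as-treated signed-rank sentence in 9.1 and the data-driven covariate rule. Report the sequence contrast descriptively. State that protection against carry-over rests on the washout and the visit-4 counter reset. The washout descriptions must be reconciled: the synopsis has patients stop study drug, while 4.2 gives placebo.

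The cost is wording in three places, by amendment before unblinding, with no new data or visits. The plan would rely openly on the washout, and the rank test would lose about 1-2 points of power if the data are normal.

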6.1.1 Treatment assignment

This study will be double blind. At the Baseline/randomization visit, qualified patients will be randomly assigned in a 1:1 ratio to either empagliflozin at a dose of 10 mg/day or placebo (study drug packages will be identical for all treatments).

Each patient's treatment will be assigned manually on the basis of a pre-determined randomization schedule prepared by the data management of the study CRO (_____). The randomization code will be generated and stored under secure and blinded conditions. The randomization will include stratification logarithm by ischemic versus non-ischemic cardiomyopathy and PVC burden at screening of $<$ or \geq to 4%

Each subject will be assigned a subject screening number.

The screening number will be structured so that each subject participating in the study will have a unique number. Screening number must not be re-used for different subjects. In case a subject is re-screened, the initial screening number should be retained and used.

Once subject's eligibility is confirmed, a subject will be assigned with a unique randomization number and will be randomized to treatment arm according to the randomization list Randomization number which will start with an RND or ENR followed by the site number and 3 digit subject number (for example – RND/ENR01-001, RND/ENR01-002 etc. for site number 1, etc.)

A dedicated "Subject Identification Log" will be kept at site. This log will include the subject's identifying details (e.g. name, ID number, telephone number) together with the screening and randomization number (if applicable).

The "Subject Identification Log" will be kept only at the investigational site and will not be taken out of the site.

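### If carry-over is declared, the fallback mixed model picks its covariates from the data and omits both randomisation strata

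*Combined protocol and SAP*

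**What the plan says.** Section 9.2.1 begins with a carry-over test comparing the two sequences. If it shows nothing: "If no carry-over effect will be observed, then The Paired T-test or non-parametric Signed-rank test for two means (as is appropriate) will be applied". If it is significant: "Otherwise, if a carry-over effect will be found statistically significant, then the MMRM model (Mixed-effect model for repeated measures) will be applied".

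The MMRM terms are then listed: "The model will included terms for study arm (sequence), treatment and period as fixed effects, and subject nested within study arm as a random effect". The next sentence adds the covariate rule: "Other covariates (such as age and baseline measures) will be included if they will be found different between the groups and affecting the outcome". The section does not say which test or cut-off decides either condition, whether groups means sequences or treatments, which covariates beyond the two examples are candidates, or which visit supplies the baseline measures.

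On allocation, section 6.1.1 says: "The randomization will include stratification logarithm by ischemic versus non-ischemic cardiomyopathy and PVC burden at screening". The cut for PVC burden is 4%. Neither factor appears among the MMRM terms.

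**The concern.** Whether a covariate affects the outcome can be judged only from outcome data, and whether groups differ only from the data collected. A rule that needs both leaves the model unspecified until the data are in. With no threshold and no closed list, two analysts could follow it and report different models.

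The rule also works against the factors with the best claim to inclusion. Blocked, stratified randomisation is meant to balance aetiology and the 4% burden class between sequences. They will therefore seldom be found different, and the rule will tend to leave them out. The covariates it admits will mostly be chance imbalances.

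At stake are the reproducibility of the primary result in the carry-over branch, and a little precision when some patients contribute only one period.

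**Working it through.** **1. The plan's own figure.** Inputs from section 9.1: difference 10, SD of differences 40, two-sided alpha 0.05, power 80%.

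- Normal approximation: N = (40 × (1.960 + 0.842) / 10)² = 125.6, so 126.
- Exact noncentral t: N = 128, power 80.1%.
- The stated 28.284 is the root MSE: 28.284 × √2 = 40.0.

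The planned 128 reproduces. It involves no covariates, so fixing them leaves it unchanged.

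**2. Where the rule applies.**

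| Carry-over test | Primary analysis | Covariate selection | Strata in analysis |
|---|---|---|---|
| Not significant | Paired t or signed-rank | None | No |
| Significant | MMRM | By the conditional rule | No |

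**3. Complete pairs.** Write a patient's reading in period j as sequence + period + treatment + γx + u + e, where x is a patient-level covariate and u the patient effect. The period 2 minus period 1 difference contains neither γx nor u, so x cannot move the treatment contrast. In one simulated trial of 128 with complete data, the estimate was −9.08 (SE 3.36) with no covariate, with one covariate, and with that covariate plus two strata.

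**4. Missing second periods.** Let σ² be the variance of a period reading, ρ the between-period correlation, m the share of period 2 missing (at random, equal in both sequences) and n the number per sequence. With sequence, period and treatment in the model, the GLS variance of the period difference within a sequence is

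V = (σ²/n) × [(1 − ρ²)/(1 − m) + (1 − ρ)²].

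The treatment contrast is half the difference between the sequences, so the SE ratio is √(V adjusted / V unadjusted). Assume visit 2 burden correlates r with each period and that ρ = r. Unadjusted: σ² = 1, ρ = r. Adjusted: σ² = 1 − r², ρ = r/(1 + r). The documents give neither r nor m.

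For r = 0.7, m = 0.2:
- Unadjusted nV = 0.51/0.8 + 0.09 = 0.7275.
- Adjusted nV = 0.4235/0.8 + 0.1765 = 0.7059.
- Ratio = √(0.7059/0.7275) = 0.985.

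| r | m | nV unadjusted | nV adjusted | SE reduction |
|---|---|---|---|---|
| 0.7 | 0 | 0.6000 | 0.6000 | 0% |
| 0.7 | 0.1 | 0.6567 | 0.6471 | 0.7% |
| 0.7 | 0.2 | 0.7275 | 0.7059 | 1.5% |
| 0.7 | 0.3 | 0.8186 | 0.7815 | 2.3% |
| 0.5 | 0.2 | 1.1875 | 1.1667 | 0.9% |
| 0.5 | 0.3 | 1.3214 | 1.2857 | 1.4% |

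**5. Movement of the estimate.** With about 14% of period 2 removed from the simulated trial, the three models gave −8.06, −7.70 and −7.85, each with SE about 3.6. The largest move, 8.06 − 7.70 = 0.36, is about a tenth of a standard error.

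**6. Type I error.** A null simulation of 6,000 trials per setting assumed three period-specific baseline covariates, with both screens at p < 0.05. It did not condition on the carry-over test. Monte Carlo error is about 0.3 points.

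| Correlation with outcome difference | Rule adds a covariate | Rule followed mechanically | Covariates always in | Most favourable of three models reported |
|---|---|---|---|---|
| 0 | 0.7% | 4.9% | 4.8% | 5.4% |
| 0.3 | 13.3% | 4.3% | 4.9% | 7.2% |
| 0.5 | 14.6% | 3.6% | 5.0% | 8.8% |

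The three models in the last column are unadjusted, rule-selected and fully adjusted. The rule itself does not inflate error; an open choice among models would. The simulated covariates change between periods, so by step 3 these figures do not carry over to a single visit 2 baseline with complete pairs.

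**The case against.** The strongest reply is that this is a minor gap in a fallback. If carry-over is not declared, the primary test has no covariates and nothing to select. In the fallback, patient-level covariates do nothing to the treatment contrast in complete pairs, and the gain with missing data is a percent or two under assumed inputs. Followed as written, the rule showed no inflation of type I error. All of that stands, and it limits the weight of the point. It does not justify keeping a rule that leaves the model open when the candidate variables are already collected.

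The documents do not support four stronger readings:

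- **That the primary model depends on unblinded outcome data.** The plan does not say when or by whom covariates are screened. Imbalance could be checked on masked sequence labels and association on pooled data. The rule is data-dependent; nothing shows it is unblinded.
- **That the primary analysis as a whole is chosen by this rule.** It governs the MMRM only.
- **That the visit 4 reading will enter as a baseline.** Sections 4.2.2 and 6.1.1 place baseline at visit 2, and section 7.1 gives visit 4 burden no analytic purpose. The device is interrogated at visit 4, after period 1 treatment, so a misreading is possible and worth closing off.
- **That the precision to be gained in the carry-over comparison measures the harm here.** That comparison is a separate unadjusted two-sample test, which the covariate sentence does not govern. Whether to adjust it is a different question.

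**Conclusion.** The point holds, at modest weight. In the branch reached after a significant carry-over test, the MMRM's covariates are chosen from the data by an unquantified rule, and both randomisation strata are left out. The treatment standard error changes by 0% with complete pairs. With visit 2 burden fixed in the model it falls by about 1.5% to 2.3%, assuming correlation 0.7 and 20% to 30% of period 2 missing at random, and by less at lower values of either. Some missing pairs are plausible: section 4.4.1 does not replace withdrawals, and the ITT definition in section 9.2 requires only one post-baseline assessment. The larger benefit of a fixed model is that the reported analysis no longer depends on an undefined choice. No bias or type I inflation has been shown for the rule applied mechanically.

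**What to change.** In section 9.2.1, delete the conditional covariate sentence and state:

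- The MMRM terms are sequence, period, treatment, aetiology (ischaemic or not) and visit 2 pre-dose PVC burden as a continuous covariate, with subject within sequence as a random effect.
- Baseline means visit 2. Readings taken after first dosing, including visit 4, are not covariates.
- Which reading defined the 4% stratum. Section 7.1 evaluates burden at visit 1 for device function and at visit 2 for eligibility, so screening burden could be either. If it was not the visit 2 reading, keep the 4% indicator as well.

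The cost is two degrees of freedom (three with the indicator) and an amendment to the plan. All the variables are already collected and the sample size stays at 128. The paired or signed-rank branch and the carry-over test are not touched by this change.
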